6.1 Demographic and Baseline Characteristics

The following demographic and baseline characteristics will be summarized for each treatment group, and for overall subjects the Stand-Alone data set.

- Gender (male, female)
- Race (white, black, American Indian/Alaska native, Native Hawaiian or another Pacific Islander, Asian, Other, Multi-Race)
- Ethnicity (Hispanic or Latino)
- Age (years)
- Age group (≤ 65 , > 65)
- Weight for all subjects (kg)
- Weight for all male subjects (kg)
- Weight for all female subjects (kg)
- Height (cm)
- Body mass index (BMI, kg/m^2)
- Body mass index category (BMI, kg/m^2) (≤ 25 , > 25)

Alcohol and tobacco use will be summarized for each treatment group and overall subjects for the Stand-Alone safety data set. For alcohol use, the number and percentage of subjects who are drinkers, ex-drinkers and non-drinkers (defined as those who have never been a drinker) will be presented. For tobacco use, the number and percentage of users, ex-users and non-users (defined as those who have never been a user) will be presented. A subject reporting multiple use category for the different types of tobacco (cigarette, pipe, cigar and chewing tobacco) will be counted in the tobacco user category.

The following baseline efficacy and clinical variables will be summarized for each treatment group and overall subjects for the ITT data set and Delayed-Start data set (if Delayed-Start analysis will be conducted).

- PSPRS total and domain scores
- UPDRS Part II score
- SEADL score
- CGI-S score
- RBANS total scale score
- Color Trails Test (Parts 1 and 2) score
- Letter Fluency Test score
- NNIPPS-PPS total score
- EQ-5D index score and VAS score

Categorical variables will be summarized by the number and percentage of subjects in each category. No comparisons of treatment groups will be performed for alcohol and nicotine uses. Continuous variables will be summarized with descriptive statistics (number of non-missing observations, mean, standard deviation, median, minimum and maximum). No statistical comparisons of treatment groups will be performed.

6.2 Medical History

Medical history of this study is transferred from medical history in Study M15-562. The conditions/diagnoses recorded in medical/surgical history data will be coded using the most current version of the Medical Dictionary for Regulatory Activities (MedDRA). Data will be summarized and presented using system organ classes (SOCs) and preferred terms (PTs). The SOC will be presented in alphabetical order and the PTs will be presented in alphabetical order within each SOC. The number and percentage of subjects with any condition/diagnosis and condition/diagnosis in a particular SOC and PT will be summarized for each treatment group and overall subjects for the safety Stand-Alone data set. Subjects reporting more than one PT within a SOC will be counted only once for that SOC. No comparison among treatment groups will be performed.

The following progressive supranuclear palsy disease history variables will be summarized for each treatment group and overall subjects for the Stand-Alone data set.

- Age at onset of symptoms of PSP (years)
- Age when first diagnosed as having PSP (years)
- Years since onset of PSP symptoms (Age at study – Age at onset)
- Years since PSP diagnosis (Age at study – Age at diagnosis)
- Family history of PSP (None, biological mother, biological father, full sibling, biological child)

Categorical variables will be summarized with the number and percentage of subjects in each category. Continuous variables will be summarized with descriptive statistics (number of non-missing observations, mean, standard deviation, median, minimum, and maximum). No comparisons of treatment groups will be performed.

6.3 Previous and Concomitant Medications

Previous medications are defined as all medications with a start date before the first study drug administration date. Concomitant medications are defined as all medications, other than study drug, taken during the treatment period (i.e., from the first day of study drug administration through 45 days after the last day of study drug administration). Previous and concomitant medications will be coded using the World Health Organization (WHO) dictionary and will be summarized by generic name and Anatomical Therapeutic Chemical (ATC) classification system level 3. The number and percentage of subjects who take at least 1 medication and who take at least 1 dose of each specific medication in the following categories will be summarized for each treatment group and overall subjects for the Stand-Alone data set.

- Previous medications for PSP (CMCAT = "PROGRESSIVE SUPRANUCLEAR PALSY MEDICATIONS") will be summarized by the following categories:
 - Antipsychotic medication

- Antidepressants
- Medications for Parkinsonian symptoms (including levodopa/carbidopa, dopamine agonists, monoamine oxidase inhibitors, COMT inhibitors, and amantadine).
- Anti-dementia drugs (CMCLAS3 = ANTI-DEMENTIA DRUGS): cholinesterase inhibitors (donepezil, rivastigmine, galantamine) or memantine for cognitive impairment.
- Selective benzodiazepines and gamma-aminobutyric acid (GABA) agonists (zolpidem, zaleplon, eszopiclone, alprazolam, clonazepam and lorazepam for sleep and anxiety). Other medications
- Other previous medications
- Concomitant medications for PSP (CMCAT = "PROGRESSIVE SUPRANUCLEAR PALSY MEDICATIONS") will be summarized by the same categories as previous medications for PSP.
- Concomitant non-medicinal therapy.
- Other concomitant medications.

No comparisons of treatment groups will be performed.

7.0 Subject Disposition

For subjects who are enrolled in the study, the number and percentage of subjects in each disposition category (prematurely discontinued and completed) will be summarized for each treatment group and overall subjects. The interim analyses, the disposition category "ongoing" will also be included.

The number and percentage of subjects who prematurely discontinued study drug or prematurely discontinued from the study will be summarized by reason (primary or any reason) for each treatment group and overall subjects.

In addition, the following additional summaries will be presented for all enrolled subjects:

- The number and percentage of subjects who are enrolled at each site.

- The number and percentage of subjects who prematurely discontinued at each site.

8.0 Study Drug Exposure and Compliance

Summaries of study drug exposure and compliance will be prepared for the Stand-Alone data set.

Study drug exposure will be summarized for each treatment group and overall subjects. Duration of exposure is calculated as the last study drug administration date minus the first study drug administration date + 30. Total subject years of exposure is calculated by summing the duration of exposure across all subjects and dividing this sum by 365 (1 year will be considered as 365 days). The number and percentage of subjects who have taken a total of ≤ 6 , 7 to 12, 13 to 18, 19 to 24, 25 to 30, 31 to 36, 37 to 42, 43 to 48, 49 to 54, 55 to 60, and ≥ 61 doses of study drug will be summarized. No comparisons of treatment groups will be performed for this summary. In addition, duration of exposure will be summarized with descriptive statistics (number of non-missing observations, mean, standard deviation, median, minimum and maximum duration and total years).

At each scheduled dosing visit, the investigator will document whether the subject has received entire infusion and the volume administered will be recorded in the eCRF if the entire dose is not administered. The percentage of the assigned dose administered will be calculated. The mean of this percentage across infusions for each subject will be obtained. The descriptive statistics (number of non-missing observations, minimum, mean, median, standard deviation, maximum) based on each subject's mean volume percentage of study drug infusion will be summarized for each treatment group and overall subjects.

9.0 Efficacy Analysis

No efficacy analyses will be conducted. Baseline values and change from baseline of the following primary and secondary efficacy variables will be summarized on both ITT data set and Delayed-start data set:

- PSPRS total score
- UPDRS Part II score
- CGI-C score
- SEADL score
- CGI-S score
- PGI-C score
- PSP-SS (composite of items from PSPRS) score

A Figure of mean of PSPRS total score for each visit will be displayed by treatment groups 2000/2000 mg, 4000/4000 mg, placebo/2000 mg, and placebo/4000 mg. This will be conducted on delayed-start data set.

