8.0 Statistical Methods and Determination of Sample Size

The data analysis will be grouped by assigned treatment sequences/group in Studies M15-562/M15-563: 2000/2000 mg, 4000/4000 mg, placebo/2000 mg, and placebo/4000 mg. If the treatment effect between each ABBV-8E12 dose and placebo is statistically significant at Week 52 in Study M15-562, the 2000/2000 mg and 4000/4000 mg groups could be combined as the early-start ABBV-8E12 treatment group, and the placebo/2000 mg and placebo/4000 mg groups could be combined as the delayed-start group for the delayed-start analysis. Details of the analyses will be specified in the statistical analysis plan (SAP).

Data Sets for Efficacy Analyses

Two data sets will be used for the efficacy analysis: an intent-to-treat (ITT) data set and a delayed-start data set.

ITT Data Set: The Study M15-563 ITT data set consists of all subjects who received any dose of study drug in Study M15-563. This is the primary efficacy analysis set for this

study. All efficacy analyses for Study M15-563 alone will be conducted on the ITT set unless otherwise specified.

Delayed-Start Data Set: The delayed start analysis data set includes efficacy data from both Studies M15-562 and M15-563. All subjects from Study M15-562 ITT data set will be included, regardless if they enroll in Study M15-563 or not. Subjects who complete Study M15-562 and rollover to Study M15-563 but have a gap of more than 8 weeks between study drug infusions before enrolling into Study M15-563 will be excluded from this analysis set.

Data Sets for Safety Analyses

The safety data sets will consist of all subjects who received any dose of study drug in Study M15-563. For the safety analyses, the actual treatment received will be used instead of the treatment assignment at the time of randomization. There are 2 safety datasets: a Stand-Alone safety data set and a cumulative safety data set as described below.

Stand-Alone Data Set: The stand-alone data set is the primary data set for the safety analysis, and will contain data from Study M15-563 only, regardless of the treatment received in Study M15-562. Baseline will be the last observation on or before the first dose of ABBV-8E12 in Study M15-563. If no Baseline is recorded in Study M15-563, the last value in Study M15-562 will be used as the Baseline.

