8.1 Statistical and Analytical Plans

8.1.1 Efficacy Analyses

All efficacy analyses of comparisons will be performed with a 2-sided test at the significance level of 0.05 unless otherwise specified. All efficacy assessments that are taken no more than 45 days after the last dose of study drug will be included in the efficacy analysis.

The primary efficacy variable is the PSPRS total score in the Study M15-563 ITT analysis. The primary analysis model is a likelihood-based, mixed-effect model, repeated measures (MMRM) analysis of the PSPRS total score at Study M15-563 Baseline and each post-baseline observation using all observed data. The model will consist of fixed, categorical effects for treatment, site, visit, and treatment-by-visit interaction. An unstructured (co)variance structure will be used to model within-subject errors. Satterthwaite's approximation will be used to estimate denominator degrees of freedom, and the Type III sum-of-squares for the Least Square (LS) means will be used to estimate treatment group differences. The differences for placebo/2000 mg vs 2000/2000 mg and for placebo/4000 mg vs 4000/4000 mg at Study M15-563 Baseline and at the end of the Study M15-563 Treatment Period will be presented with a 95% confidence interval. Contrasts of treatment effects for other visits will be conducted as well. This MMRM analysis will be applied to each efficacy variable with repeated measurements. Details of the analysis will be described in the SAP.

The delayed-start analysis will be conducted on the change from Baseline in Study M15-562 up to Week 52 in Study M15-563 on the PSPRS total score. An MMRM analysis model will be used. The model will consist of fixed, categorical effects for treatment, site, visit, and treatment-by-visit interaction, with continuous fixed covariates for baseline PSPRS total score and the baseline score-by-visit interaction. An unstructured (co)variance structure will be used to model within-subject errors. Satterthwaite's approximation will be used to estimate denominator degrees of freedom, and the Type III sum-of-squares for the LS means will be used to estimate treatment

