group differences. The primary comparisons will be the contrasts between an ABBV-8E12 dose group and the placebo group at Week 52 in both Study M15-562 and Study M15-563, and non-inferiority analysis of treatment effects at Week 52 between the 2 studies. If only one of the ABBV-8E12 dose groups in Study M15-562 is statistically significantly different from placebo at Week 52, the delayed-start analysis will be conducted only for that dose. If treatment effects at Week 52 in Study M15-562 are statistically significant for both ABBV-8E12 doses (based on the primary analysis defined in the Study M15-562 SAP), the combined early-start groups and the combined delayed-start groups will be used for the delayed-start analysis. If neither ABBV-8E12 dose is statistically significantly different from the placebo at Week 52 in Study M15-562, the delayed-start analysis will not be conducted. No multiplicity adjustment will be made for the delayed-start analysis based on combined groups or a selected ABBV-8E12 dose. Details of the analysis will be specified in the SAP.

The analysis on secondary and exploratory efficacy variables will be detailed in the SAP.

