Appendix C. Criteria for Potentially Clinically Significant ECG Values54

3.0 Introduction

This analysis plan describes the statistical analyses to be completed by AbbVie Statistical Science and Programming for ABBV-8E12 Study Protocol M15-563, that incorporates two amendments (original Protocol, Amendment 1, Administrative Change 1, Amendment 2, Administrative Change 2).

This statistical analysis plan (SAP) provides details to further elaborate statistical methods as outlined in the protocol and describes analysis conventions to guide the statistical programming work. Population pharmacokinetic and exposure-response analysis for this study, if performed, will be conducted separately and are not included in this SAP.

Analyses will be performed using SAS version 9.3 or higher (SAS Institute Inc., Cary, NC 27513) under the UNIX operating system.

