4.0 Study Objectives, Design and Procedures

4.1 Objectives

The primary objectives of this study are:

- To assess the long-term safety and tolerability of ABBV-8E12 in subjects with progressive supranuclear palsy (PSP).
- To assess the long-term efficacy of ABBV-8E12 in slowing disease progression in subjects with PSP as measured by the PSP Rating Scale (PSPRS).

The secondary objectives of this study are:

- To assess the long-term efficacy of ABBV-8E12 in slowing disease progression and functional impairment in subjects with PSP as measured by secondary endpoints.
- To assess the pharmacokinetics of ABBV-8E12 in subjects with PSP.

- To assess the long-term efficacy of ABBV-8E12 in slowing regional and/or whole brain atrophy in subjects with PSP as measured by volumetric magnetic resonance imaging (MRI).

The exploratory objectives of this study are:

- To assess the long-term efficacy of ABBV-8E12 in slowing disease progression and functional impairment in subjects with PSP as measured by exploratory endpoints.
- To assess the long-term effect of ABBV-8E12 on cerebrospinal fluid (CSF) and plasma tau protein levels.
- To assess the long-term effect of ABBV-8E12 on other potential CSF and plasma biomarkers of disease progression.
- To assess body position and gait in a subset of participating subjects using BioStamp digital sensors.

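### SAP 9.0 cancels the protocol's unconditional primary PSPRS model, so a primary objective has no planned between-group estimate or confidence interval, and the available text gives no reason

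*SAP*

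**What the plan says.** **Protocol.** Section 8.1.1 takes PSPRS total score in the Study M15-563 ITT set as the primary efficacy variable and states: "The primary analysis model is a likelihood-based, mixed-effect model, repeated measures (MMRM) analysis of the PSPRS total score". Section 8.0 says of that ITT set: "This is the primary efficacy analysis set for this" study. The required output is specific: "The differences for placebo/2000 mg vs 2000/2000 mg and for placebo/4000 mg vs 4000/4000 mg at Study M15-563 Baseline" and again at the end of the Treatment Period, each with a 95% confidence interval. Section 8.1.1 adds: "Contrasts of treatment effects for other visits will be conducted as well".

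The same section attaches a condition to one other analysis only: "If neither ABBV-8E12 dose is statistically significantly different from the placebo at Week 52 in Study M15-562, the delayed-start analysis will not be conducted".

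**SAP.** Section 3.0 describes its role thus: "This statistical analysis plan (SAP) provides details to further elaborate statistical methods as outlined in the protocol". Section 4.1 keeps as one of two primary objectives: "To assess the long-term efficacy of ABBV-8E12 in slowing disease progression in subjects with PSP as measured by the PSP Rating Scale (PSPRS"). Section 4.5 says the PSPRS total score will serve to assess the treatment effect, and Section 5.1 assigns efficacy analyses to the ITT set. Section 9.0 then opens: "No efficacy analyses will be conducted". It leaves summaries of baseline and change from baseline for seven efficacy variables, and one figure of mean PSPRS by visit and treatment sequence.

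**The concern.** The two governing documents disagree on whether the primary efficacy analysis exists. The protocol leaves the details of that analysis to the SAP. It does not leave open whether to run it.

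If the SAP is followed, one of the two primary objectives is reported without a difference between the early-start and delayed-start sequences and without a planned measure of its uncertainty. The PSPRS data are collected either way. Mean curves by sequence invite a visual comparison, and the plan provides no interval to show how imprecise that comparison is. The SAP also disagrees with itself: Sections 4.1, 4.5 and 5.1 presume an analysis that Section 9.0 withdraws.

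**Working it through.** The point rests on the text. The documents state no power, effect size or standard deviation for this study, so there is no figure of the plan's to reproduce.

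**1. Is the protocol's model conditional?** No. The rule that cancels an analysis when neither dose beats placebo in Study M15-562 names the delayed-start analysis. That is a different model: it covers change from the Study M15-562 baseline up to Week 52 of Study M15-563, on the Delayed-Start set. The ITT model has no such rule. A negative Study M15-562 would remove the first and leave the second standing.

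**2. What is lost?**

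| Item | Protocol 8.1.1 | SAP 9.0 |
|---|---|---|
| Model for PSPRS | Repeated-measures, ITT set | None |
| Named contrasts | 2 | 0 |
| Named time points with 95% CI | 2 (Baseline, end of treatment) | 0 |
| Named estimates with CI | 2 × 2 = 4 | 0 |
| Contrasts at other visits | Yes | None |

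**3. What could a reader still recover?** SAP 6.1 lists PSPRS total score among the baseline variables summarized by treatment group on the ITT set, and it gives the number of observations, mean and standard deviation for continuous variables. SAP 5.1 bases ITT efficacy work on Study M15-563 data alone unless stated otherwise. From those three statistics a reader could compute an unadjusted difference and interval at Study M15-563 Baseline. For later visits SAP 9.0 promises summaries but does not list the statistics. No between-group estimate or interval is planned at any visit.

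**4. Is the SAP descriptive throughout?** No, but the pattern is mixed. SAP 12.2 keeps a repeated-measures model for CSF and plasma tau, an exploratory objective, with a test of the two doses at the 0.050 level. It keeps a corresponding model for imaging variables, and volumetric MRI is a secondary objective. Against that, SAP 10.1 drops the between-group safety comparisons that Protocol 8.1.2 had planned.

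**5. Is a departure declared?** The available SAP text has no section on changes from the protocol and gives no reason. SAP 3.0 cites Administrative Change 2, which was not available, and neither was the SAP title page.

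**6. Can the protocol's model be fitted as written?** PSPRS is scheduled at 12 treatment-period visits (Protocol Table 3: Day 1 and Weeks 12, 24, 52, 76, 104, 128, 156, 180, 208, 232 and 260). An unstructured covariance matrix over 12 visits has 12 × 13 / 2 = 78 parameters. The fixed effects include site, at about 60 sites (Protocol 5.1), and treatment by visit, 4 × 12 = 48 cells. The sample cannot exceed 378 and will shrink over up to five years. Convergence is a real risk, and Protocol 8.1.1 names no fallback.

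**The case against.** The best defense is that the sponsor moved deliberately to description of clinical outcomes. The safety comparisons were dropped too, no power was ever set for this extension, and late-visit contrasts may carry little information. On that view only a wording change is needed, and reinstating the model is a preference. Much of this stands. A descriptive report is a legitimate choice, and declaring it would resolve the conflict. It would still have to be declared, and SAP 4.1, 4.5 and 5.1 would have to change with it.

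The fitting problem in step 6 is also a fair objection to simply restoring the protocol text. It calls for a fallback and does not justify silence.

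Three stronger readings are tempting, and the documents do not support them:

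- **That no measure of uncertainty can be obtained at all.** SAP 6.1 plans the number of observations, mean and standard deviation at baseline, so an unadjusted baseline interval can be derived.
- **That exploratory tau receives the very inference denied to PSPRS.** The SAP 12.2 models compare 2000 mg with 4000 mg among subjects already on active drug in Study M15-562. They do not compare early with delayed start.
- **That the departure was concealed, or followed from the Study M15-562 result.** The documents give no motive, and a reason may stand in material that was not available.

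**Conclusion.** The conflict is real and has to be resolved before the analysis. Protocol 8.1.1 requires the PSPRS model without condition, and SAP 9.0 removes it while the rest of the SAP still presumes it. All four of the protocol's named estimates are lost, along with the contrasts at other visits, for one of two primary objectives.

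The conclusion depends on no assumed number. How wide the intervals would be cannot be stated from the documents: they give a ceiling of 378 subjects but no standard deviation, rollover rate or retention. Late-visit intervals should be expected to be wide. The statement that no reason is given is limited to the text available.

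**What to change.** **Preferred.** In SAP 9.0, reinstate the Protocol 8.1.1 PSPRS model on the ITT set as estimation without formal testing:

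- Report placebo/2000 mg versus 2000/2000 mg and placebo/4000 mg versus 4000/4000 mg, with 95% confidence intervals and the number of subjects per visit, at Study M15-563 Baseline, Week 52 and the end of treatment (or the last visit with adequate data).
- Name in advance a fallback covariance structure and a site-pooling rule for use if the unstructured model does not converge. SAP 12.2 already defines simpler structures. Its heterogeneous compound symmetry option would need 12 variances + 1 correlation = 13 parameters in place of 78, although it assumes equal correlation between all pairs of visits.
- State that the analysis conditions on rollover: the ITT set holds only subjects dosed in Study M15-563, so the contrasts are no longer between the full groups randomized in Study M15-562.

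The cost is SAP wording and one extra model, with wide intervals at late visits. No new data are needed.

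**Alternative.** If no efficacy conclusion is intended, declare the departure from Protocol 8.1.1 in the SAP with its reason, or cite where it is already declared, and align SAP 4.1, 4.5 and 5.1. This costs wording only, and the primary efficacy objective would then be described without a between-group estimate.
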